6.1.2 CAEPR for ipilimumab (MDX-010, NSCs 732442 and 720801)

The CAEPR provides a single list of reported and/or potential adverse events (AE) associated with an agent using a uniform presentation of events by body system. In addition to the comprehensive list, a subset, the SPEER, appears in a separate column and is identified with bold and italicized text. This subset of AEs (SPEER) is a list of events that are protocol-specific exceptions to expedited reporting to NCI (except as noted below). Refer to the 'CTEP, NCI Guidelines: Adverse Event Reporting Requirements'

http://ctep.cancer.gov/protocolDevelopment/electronic_applications/docs/aeguidel ines.pdf_for further clarification. *Frequency is provided based on 2678 patients*. Below is the CAEPR for Ipilimumab (MDX-010).

NOTE: Report AEs on the SPEER ONLY IF they exceed the grade noted in parentheses next to the AE in the SPEER. If this CAEPR is part of a combination protocol using multiple investigational agents and has an AE listed on different SPEERs, use the lower of the grades to determine if expedited reporting is required.

Version 2.10, March 29, 2019¹

Adverse Events with Possible Relationship to Ipilimumab (MDX-010) (CTCAE 5.0 Term) [n= 2678]		Specific Protocol Exceptions to Expedited Reporting (SPEER)	
Likely (>20%)		Rare but Serious (<3%)	
BLOOD AND LYMPHA	TIC SYSTEM DISORDERS		
		Blood and lymphatic system disorders - Other (acquired hemophilia)	
CARDIAC DISORDERS			
	Atrial fibrillation		
		Myocarditis ²	
		Pericardial effusion	
EAR AND LABYRINTH	DISORDERS		
	Hearing impaired		
ENDOCRINE DISORDE	RS		
	Adrenal insufficiency ²		
	Hyperthyroidism ²		
	Hypophysitis ²		
	Hypopituitarism ²		
	Hypothyroidism ²		
	Testosterone deficiency ²		
EYE DISORDERS	,	•	
	Eye disorders - Other (episcleritis) ²		
	Uveitis ²		
GASTROINTESTINAL I	DISORDERS	•	
	Abdominal pain		
j	Colitis ²		Colitis (Gr 3)
		Colonic perforation ³	
	Constipation		
Diarrhea			Diarrhea (Gr 3)
	Enterocolitis		
	Esophagitis		
		Ileus	
Nausea			Nausea (Gr 3)

Adverse Events with Possible Relationship to Ipilimumab (MDX-010) (CTCAE 5.0 Term) [n= 2678]		Specific Protocol Exceptions to Expedited Reporting (SPEER)	
Likely (>20%)	Less Likely (<=20%)	Rare but Serious (<3%)	
	Pancreatitis ²		
	Vomiting		
GENERAL DISORDERS	S AND ADMINISTRATION SITE COND	ITIONS	
	Chills		
Fatigue			Fatigue (Gr 3)
1 augue	Fever		Fever (Gr 2)
		General disorders and administration site conditions - Other (systemic inflammatory response syndrome [SIRS])	20101 (01.2)
IIIDA TODII IADII DIG	ORDERG	Multi-organ failure	
HEPATOBILIARY DIS	Hepatobiliary disorders - Other (hepatitis) ²		
IMMUNE SYSTEM DIS	Autoimmune disorder ²	1	
	Autoimmune disorder	Immune system disorders - Other (GVHD in the setting of allotransplant) ⁴	
INFECTIONS AND INF	ESTATIONS		
		Infections and infestations - Other (aseptic meningitis) ²	
INJURY, POISONING A	ND PROCEDURAL COMPLICATIONS		
	Infusion related reaction		
INVESTIGATIONS			
	Alanine aminotransferase increased		
	Aspartate aminotransferase increased		
		Lymphocyte count decreased	
	Neutrophil count decreased		
	Weight loss		
METABOLISM AND N	UTRITION DISORDERS		
	Anorexia		
	Dehydration		
	Hyperglycemia	Metabolism and nutrition disorders - Other (exacerbation of pre-existing diabetes mellitus)	
MUSCULOSKELETAL .	AND CONNECTIVE TISSUE DISORDE	RS	
	Arthralgia		
	Arthritis		
		Generalized muscle weakness	
	Musculoskeletal and connective tissue disorder - Other (polymyositis) ²		
NERVOUS SYSTEM DI	SORDERS		
		Ataxia	
	Facial nerve disorder		
	Guillain-Barré syndrome ²		
	Headache		
	Myasthenia gravis ²		

Adverse Events with Possible Relationship to Ipilimumab (MDX-010) (CTCAE 5.0 Term) [n= 2678]		Specific Protocol Exceptions to Expedited Reporting (SPEER)	
Likely (>20%)	Less Likely (<=20%)	Rare but Serious (<3%)	
		Nervous system disorders - Other (immune-mediated encephalitis) ²	
		Peripheral motor neuropathy	
		Peripheral sensory neuropathy	
	Trigeminal nerve disorder		
PSYCHIATRIC DISORDI	ERS		
		Psychiatric disorders - Other (mental status changes)	
RENAL AND URINARY	DISORDERS		
	Acute kidney injury		
	Renal and urinary disorders - Other (granulomatous tubulointerstitial nephritis)		
RESPIRATORY, THORA	CIC AND MEDIASTINAL DISORDER	S	
	Pneumonitis		
		Respiratory failure	
		Respiratory, thoracic, and mediastinal disorders - Other (bronchiolitis obliterans with organizing pneumonia)	
		Respiratory, thoracic, and mediastinal disorders - Other (lung infiltration)	
SKIN AND SUBCUTANE	EOUS TISSUE DISORDERS		
	 	Erythema multiforme	
	Pruritus	-	Pruritus (Gr 3)
Rash maculo-papular	1		Rash maculo-papular (Gr 3)
	Skin and subcutaneous disorders - Other (Sweet's syndrome)		
		Stevens-Johnson syndrome	
	4	Toxic epidermal necrolysis	
	Urticaria		
VASCULAR DISORDER		,	
	Hypotension		

¹This table will be updated as the toxicity profile of the agent is revised. Updates will be distributed to all Principal Investigators at the time of revision. The current version can be obtained by contacting [contact]. Your name, the name of the investigator, the protocol and the agent should be included in the e-mail.

²Ipilimumab can result in severe and fatal immune-mediated adverse events probably due to T-cell activation and proliferation. These can include (but are not limited to) autoimmune hemolytic anemia, acquired anti-factor VIII immune response, autoimmune aseptic meningitis, autoimmune hepatitis, autoimmune thyroiditis, hepatic failure, pure red cell aplasia, pancreatitis, ulcerative and hemorrhagic colitis, endocrine disorders (e.g., autoimmune thyroiditis, hyperthyroidism, hypothyroidism, autoimmune hypophysitis/hypopituitarism, and adrenal insufficiency), ocular manifestations (e.g., uveitis, iritis, conjunctivitis, blepharitis, and episcleritis), sarcoid granuloma, myasthenia gravis, polymyositis, and Guillain-Barre syndrome. The majority of these reactions manifested early during treatment; however, a minority occurred weeks to months after discontinuation of ipilimumab especially with the initiation of additional treatments.

³Late bowel perforations have been noted in patients receiving MDX-010 (ipilimumab) in association with subsequent IL-2 therapy.

⁴Complications including hyperacute graft-versus-host disease (GVHD), may occur in patients receving allo stem cell transplant (SCT) after receiving Ipilimumab (MDX-010). These complications may occur despite intervening therapy between receiving Ipilimumab (MDX-010) and allo-SCT.

⁵In rare cases diplopia (double vision) has occurred as a result of muscle weakness (Myasthenia gravis).

⁶Gastrointestinal hemorrhage includes Anal hemorrhage, Cecal hemorrhage, Colonic hemorrhage, Duodenal hemorrhage, Esophageal hemorrhage, Esophageal varices hemorrhage, Gastric hemorrhage, Hemorrhoidal hemorrhage, Ileal hemorrhage, Intra-abdominal hemorrhage, Jejunal hemorrhage, Lower gastrointestinal hemorrhage, Oral hemorrhage, Pancreatic hemorrhage, Rectal hemorrhage, Retroperitoneal hemorrhage, and Upper gastrointestinal hemorrhage under the GASTROINTESTINAL DISORDERS SOC.

⁷Infection includes all 75 sites of infection under the INFECTIONS AND INFESTATIONS SOC.

Adverse events reported on ipilimumab (MDX-010) trials, but for which there is insufficient evidence to suggest that there was a reasonable possibility that ipilimumab (MDX-010) caused the AE:

BLOOD AND LYMPHATIC SYSTEM DISORDERS - Anemia; Blood and lymphatic system disorders - Other (pure red cell aplasia)²; Febrile neutropenia

CARDIAC DISORDERS - Conduction disorder; Restrictive cardiomyopathy

EYE DISORDERS - Extraocular muscle paresis⁵; Eye disorders - Other (retinal pigment changes)

GASTROINTESTINAL DISORDERS - Colonic ulcer; Dyspepsia; Dysphagia; Gastrointestinal disorders - Other (gastroenteritis); Gastrointestinal hemorrhage⁶; Proctitis

GENERAL DISORDERS AND ADMINISTRATION SITE CONDITIONS - Flu like symptoms; Non-cardiac chest pain

HEPATOBILIARY DISORDERS - Hepatic failure²

IMMUNE SYSTEM DISORDERS - Allergic reaction

INFECTIONS AND INFESTATIONS - Infection⁷

INVESTIGATIONS - Creatinine increased; Investigations - Other (rheumatoid factor); Lipase increased; Platelet count decreased; Serum amylase increased; White blood cell decreased

METABOLISM AND NUTRITION DISORDERS - Tumor lysis syndrome

MUSCULOSKELETAL AND CONNECTIVE TISSUE DISORDERS - Back pain; Joint range of motion decreased; Myalgia; Pain in extremity

NEOPLASMS BENIGN, MALIGNANT AND UNSPECIFIED (INCL CYSTS AND POLYPS) - Tumor pain

NERVOUS SYSTEM DISORDERS - Dizziness; Dysphasia; Ischemia cerebrovascular; Seizure

PSYCHIATRIC DISORDERS - Anxiety; Confusion; Depression; Insomnia

RENAL AND URINARY DISORDERS - Proteinuria

RESPIRATORY, THORACIC AND MEDIASTINAL DISORDERS - Allergic rhinitis; Cough; Dyspnea; Laryngospasm

SKIN AND SUBCUTANEOUS TISSUE DISORDERS - Alopecia; Dry skin; Hyperhidrosis; Skin hypopigmentation

VASCULAR DISORDERS - Flushing; Hypertension; Vascular disorders - Other (temporal arteritis)

Note: Ipilimumab (BMS-734016; MDX-010 Transfectoma-derived) in combination with other agents could cause an exacerbation of any AE currently known to be caused by the other agent, or the combination may result in events never previously associated with either agent.

6.2 Classification of AEs by Severity and Relationship to Study Drug Administration

- 6.2.1 AE: Any unfavorable and unintended sign (including an abnormal laboratory finding), symptom or disease temporally associated with the use of a medical treatment or procedure regardless of whether it is considered related to the medical treatment or procedure (attribution of unrelated, unlikely, possible, probable, or definite).
- 6.2.2 Life threatening Adverse Event: Any AE that places the participant or participant, in view of the Investigator, at immediate risk of death from the reaction.
- 6.2.3 Serious Adverse Event (SAE): Any AE occurring at any dose that results in any of the following outcomes: Death, a life threatening AE, inpatient hospitalization, or prolongation of existing hospitalization, a persistent or significant disability/incapacity, or a congenital anomaly/birth defect.
- 6.2.4 Please note for hospitalization All hospitalizations (or prolongation of existing hospitalization) for medical events equivalent to CTCAE Grade 3, 4, 5 must be reported regardless of the requirements for Phase of study, expected or unexpected, and attribution. For example, do not report an admission for pharmacokinetic sampling, but do report an admission for a myocardial infarction.
- 6.2.5 Toxicity: Toxicity is a term NOT clearly defined by regulatory organizations. Toxicity has been described as an AE that has an attribution of possibly, probably, or definitely related to investigational treatment. To minimize confusion the NCI would recommend that the term toxicity NOT be utilized for AE reporting purposes. The CTCAE continues to use the term 'toxicity' because of familiarity.
- 6.2.6 Unexpected Adverse Event: Any AE that is not listed in available sources including the package insert, the Investigator's Brochure, or the protocol.
- 6.2.7 CTEP Adverse Event Reporting System (CTEP-AERS): An electronic system for expedited submission of AE reports.
- 6.2.8 Attribution: The determination of whether an AE is related to a medical treatment or procedure. Attribution categories:
 - Definite The AE is clearly related to the investigational agent.
 - Probable The AE is likely related to the investigational agent.
 - Possible The AE may be related to the investigational agent.
 - Unlikely The AE is doubtfully related to the investigational agent.
 - Unrelated The AE is clearly NOT related to the investigational agent.

6.3 Expedited AE Reporting

- 6.3.1 Expedited AE reporting for this study must use CTEP-AERS (CTEP Adverse Event Reporting System), accessed via the CTEP home page (http://ctep.cancer.gov). The reporting procedures to be followed are presented in the "CTEP, NCI Guidelines: Adverse Event Reporting Requirements" which can be downloaded from the CTEP home page (http://ctep.cancer.gov). These requirements are briefly outlined in the table below (Section 6.3.3).
 - A 24-hour notification is to be made to CTEP by telephone at [contact], only when Internet connectivity is disrupted. Once Internet connectivity is restored, a 24-hour notification phoned in must be entered electronically into CTEP-AERS by the original submitter at the site.
- 6.3.2 CTEP-AERS is programmed for automatic electronic distribution of reports to the following individuals: Study Coordinator of the Lead Organization, Principal Investigator, and the local treating physician. CTEP-AERS provides a copy feature for other e-mail recipients.
- 6.3.3 Expedited Reporting Guidelines

Use the NCI protocol number and the protocol-specific participant ID assigned during trial registration on all reports.

Note: A death on study requires both routine and expedited reporting regardless of causality, unless as noted below. Attribution to treatment or other cause must be provided.

Death due to PD should be reported as **Grade 5 "General disorders and administration site conditions - Disease Progression."** Evidence that the death was a manifestation of underlying disease (*e.g.*, radiological changes suggesting tumor growth or progression: clinical deterioration associated with a disease process) should be submitted.

Phase 1 and Early Phase 2 Studies: Expedited Reporting Requirements for AEs that Occur on Studies under an IND/IDE within 30 Days of the Last Administration of the Investigational Agent/Intervention ^{1,2}

FDA REPORTING REQUIREMENTS FOR SERIOUS ADVERSE EVENTS (21 CFR Part 312)

NOTE: Investigators MUST immediately report to the sponsor (NCI) ANY Serious Adverse Events, whether or not they are considered related to the investigational agent(s)/intervention (21 CFR 312.64)

An AE is considered serious if it results in **ANY** of the following outcomes:

- Death
- A life threatening AE
- An adverse event that results in inpatient hospitalization or prolongation of existing hospitalization for ≥ 24 hours
- A persistent or significant incapacity or substantial disruption of the ability to conduct normal life functions
- A congenital anomaly/birth defect.

Important Medical Events (IME) that may not result in death, be life threatening, or require hospitalization may be considered serious when, based upon medical judgment, they may jeopardize the participant or participant and may require medical or surgical intervention to prevent one of the outcomes listed in this definition. (FDA, 21 CFR 312.32; ICH E2A and ICH E6).

ALL SERIOUS adverse events that meet the above criteria MUST be immediately reported to the NCI via CTEP-AERS within the timeframes detailed in the table below.

Hospitalization	Grade 1 and Grade 2 Timeframes	Grade 3-5 Timeframes
Resulting in Hospitalization ≥ 24 hrs	10 Calendar Days	24-Hour 5 Calendar Days
Not resulting in Hospitalization ≥ 24 hrs	Not required	

NOTE: Protocol-specific exceptions to expedited reporting of SAEs are found in the SPEER portion of the CAEPR. Expedited AE reporting timelines are defined as:

- "24-Hour; 5 Calendar Days" The AE must initially be reported via CTEP-AERS within 24 hours of learning of the AE, followed by a complete expedited report within 5 calendar days of the initial 24-hour report.
- "10 Calendar Days" A complete expedited report on the AE must be submitted within 10 calendar days of learning of the AE.

¹Serious AEs that occur more than 30 days after the last administration of investigational agent/intervention and have an attribution of possible, probable, or definite require reporting as follows:

- Expedited 24-hour notification followed by complete report within 5 calendar days for:
- All Grade 3, 4, and Grade 5 AEs
- Expedited 10 calendar day reports for:
- Grade 2 AEs resulting in hospitalization or prolongation of hospitalization

Effective Date: May 5, 2011

6.4 Routine AE Reporting

All AEs that occur, regardless of attribution to the study agent, must be reported in routine study data submissions. AEs reported through CTEP-AERS must also be reported in routine study data submissions.

6.4.1 Clinical laboratory abnormalities

Clinical laboratory abnormalities will be considered AEs if determined to be clinically significant by the investigator. In assessing laboratory results, an abnormal laboratory value will be considered clinically significant if it is characterized by one or more of the following criteria:

- 1. Is not proved erroneous result by repeat testing, if performed
- 2. Is judged by the investigator to have a causal relationship to the investigational agent
- 3. Requires clinical intervention or monitoring, such as: close observation, more frequent follow-up assessments, further diagnostic intervention, treatment/therapeutic intervention, or protocol therapy dose modification

² For studies using PET or SPECT IND agents, the AE reporting period is limited to 10 radioactive half-lives, rounded UP to the nearest whole day, after the agent/intervention was last administered. Footnote "1" above applies after this reporting period.

- 4. Is associated with clinical signs or symptoms, which may suggest a disease and/or organ toxicity, or may represent a new condition or worsening of a baseline condition
- 5. Is associated with a SAEs, or is otherwise judged by the Investigator to be of significant clinical impact

In general, a laboratory abnormality that is not clinically significant will be consistent with CTCAE grade 1 (mild) or 2 (moderate) severity, as categorized by the relevant severity description in the Investigations System Organ Class (SOC) or Metabolism and Nutrition Disorders SOC. Investigators may not designate laboratory abnormalities that are consistent with grade 3 or greater severity as not clinically significant.

All laboratory values deemed clinically significant will be subsequently reported as AEs unless the result is a sign of a clinical diagnosis that is reported as an AE.

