5.0 DOSING DELAYS/DOSE MODIFICATIONS

5.1 Dose Modifications for Nivolumab and Nivolumab and Ipilimumab Combination

Participants with an overall response of SD, PR, CR, or unconfirmed PD (refer to Section 9.1 for RECIST Criteria, Section 9.2 for KS response evaluation, and Section 9.3 for the 2017 RECIL Criteria for response evaluation) at the scheduled response visits at week 8 and all subsequent visits day 1 of cycles 6 and 9 will be eligible to continue to receive study drug treatments provided that they also have an ECOG performance status score of ≤ 2 , and did not have a DLT or other safety risk requiring discontinuation of the study drugs, as defined below.

Please refer to Appendix X to the protocol for toxicity management algorithms, which include specific treatment guidelines. Where discrepancies occur between Section 5.1 and Appendix X, use the instructions in Section 5.1. These algorithms should be followed unless there are specific clinical circumstances for which the treating physician indicates variations or alternative treatment are needed.

Generally, we strongly encourage early evaluation, withholding drug, and appropriate treatment as indicated in the management tables and following event specific guidelines.

Table 2: Dose Modification Tables for Nivolumab and Nivolumab and Ipilimumab Combination

All Other Events*	Management/Next Dose for Nivolumab and Combination
≤ Grade 1	No change in dose.
Grade 2	Hold** until ≤ Grade 1 OR baseline. Resume at same dose level.
Grade 3	Hold** until ≤ Grade 1 continue at investigator discretion.
Grade 4	Off protocol therapy.

^{*} Not immunologically mediated (excluding clinically insignificant lab abnormalities, see Section 6.4.1)

Recommended management: As clinically indicated.

All Other Events**	Management/Next Dose for Nivolumab and Combination
≤ Grade 1	No change in dose.
Grade 2	Hold until \leq Grade 1 OR baseline. When resolved \leq Grade 1 and off steroids for at least 1 week, resume at same dose level.
Grade 3	Off protocol therapy (exceptions noted in 5.4). May resume nivolumab monotherapy if resolved to Grade 1 or less (off physiologic

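### Section 6.4.1 lists a precondition (not disproved on repeat testing) as a sufficient criterion, so read literally it leaves no real laboratory abnormality that is clinically insignificant

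*Combined protocol and SAP*

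**What the plan says.** Section 6.4.1 opens by giving the decision to the investigator: "Clinical laboratory abnormalities will be considered AEs if determined to be clinically significant by the investigator". It then sets the test: "an abnormal laboratory value will be considered clinically significant if it is characterized by one or more of the following criteria". Criterion 1 is "Is not proved erroneous result by repeat testing, if performed". In paraphrase, the other four are: the investigator judges the value causally related to the agent (2); it calls for intervention or monitoring, dose modification included (3); it accompanies signs or symptoms (4); it is tied to a serious AE or otherwise judged to have significant clinical impact (5).

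The section next describes values that fall outside the definition. As a rule, a value that is not "clinically significant will be consistent with CTCAE grade 1 (mild) or 2 (moderate) severity". One limit is set: "Investigators may not designate laboratory abnormalities that are consistent with grade 3 or greater severity as not clinically significant". The reporting consequence follows: "All laboratory values deemed clinically significant will be subsequently reported as AEs unless the result is a sign of a clinical diagnosis".

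Two other places depend on this definition. In Section 5.1, the Table 2 block for non-immune events under All Other Events carries the footnote "Not immunologically mediated (excluding clinically insignificant lab abnormalities, see Section 6.4.1". Section 10.1.2 plans a summary of toxicity by type and severity and points to Section 6.0 for grading and reporting.

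**The concern.** Criterion 1 reads like a data-quality check: first rule out a laboratory error, then ask whether the value matters. Placed in a list where any single item suffices, it becomes the broadest criterion of the five. A confirmed value meets it, and so does a value nobody repeated. A site that follows the list reports every mild laboratory change as an AE. A site that follows the opening sentence and the grade 1-2 paragraph reports only those it considers important. Both can claim to follow the protocol.

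At stake is the consistency of grade 1-2 laboratory counts across sites, and whether the Table 2 exclusion that cites 6.4.1 has any content.

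**Working it through.** No sample size or error rate is involved, so the check is logical. Write C1 to C5 for the five criteria.

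- As written: significant = C1 or C2 or C3 or C4 or C5.
- With C1 as a precondition: significant = C1 and (C2 or C3 or C4 or C5).

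Criteria 2 to 5 can each be met or not, giving 2 × 2 × 2 × 2 = 16 combinations.

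| | As written | C1 as precondition |
|---|---|---|
| Not disproved (C1 true) | 16 of 16 significant | 16 − 1 = 15 of 16 |
| Proved erroneous (C1 false) | 15 of 16 significant | 0 of 16 |

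These are counts of logical cases, not frequencies.

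**First row.** As written, no undisproved abnormality can be non-significant. The one case that changes meets none of criteria 2 to 5: unrelated, no symptoms, no action needed, no serious AE. That is the kind of value the grade 1-2 paragraph presupposes.

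**Second row.** As written, a disproved result could still count if, for example, it had prompted further testing. The precondition removes that oddity too.

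**By grade, for the one changed case.** At grade 3 or above, the investigator may not call the value non-significant, so it is reported under either reading. At grade 1 or 2, the literal list makes it an AE and the precondition does not. The grade 3 sentence also shows the intent: if the literal list governed, every undisproved value would already be significant and the sentence would be redundant.

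**Toxicity summary.** Section 6.4 collects all AEs regardless of attribution, and Section 10.1.2 states neither an attribution filter nor a minimum grade. Grade 1-2 laboratory counts can therefore depend on which sentence a site followed.

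**DLT and MTD.** The grade-based wording in Section 4.4 starts at grade 3, so the direct effect is negligible. An indirect route exists on paper. Section 5.1 takes a participant off protocol therapy after more than two delays for the same event, and Section 4.4 counts permanent stopping within 6 weeks as a DLT. With 2-week cycles, the dosing days after the first fall at weeks 2, 4 and 6. A third delay is therefore not reached before the window closes.

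**Table 2.** In the non-immune All Other Events block, grade 1 brings no dose change, and grade 3 or above cannot be called insignificant. The footnote's exclusion can therefore matter only at grade 2. Under the literal list, the class it excludes has no undisproved members. Criterion 3 adds a circularity: needing a dose modification makes a value significant, and significance brings it into the table that prescribes the modification.

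**The case against.** The strongest reply is that context cures the slip. The section begins with the investigator's determination, assumes a non-significant class and limits it only at grade 3. An experienced site will read criterion 1 as a check for error. Appendix VI adds quarterly AE review by the medical monitor, remote data review and audits. This makes wide divergence less likely but does not settle which sentence governs. The list is phrased as binding, and Section 6.2.1 defines an AE as "Any unfavorable and unintended sign (including an abnormal laboratory finding", which supports the literal reader. That sites actually diverge is foreseeable, not shown.

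It is also fair that the toxicity effect is not fully determined. Section 6.2.5 describes toxicity as an AE at least possibly related to treatment. If the summary is limited to such events, criterion 2 captures those values under either reading and little changes. Section 10.1.2 does not say.

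A reader might infer three stronger things that the documents do not support:

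- **That the primary conclusion is compromised.** Dose decisions rest on the DLT rule. The type-and-severity presentation is a descriptive summary.
- **That grade 2 laboratory values in general would trigger extra holds.** Only the non-immune All Other Events block cites 6.4.1. Liver, renal, amylase/lipase and endocrine events have their own rows, and the Hodgkin cohort has its own hold condition.
- **That the excess AE records per participant can be counted.** No abnormality rates are given, one persistent abnormality need not be several AEs, and criteria 2 to 5 require many grade 1-2 values to be reported under either reading.

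**Conclusion.** The contradiction is certain on the text. As written, criterion 1 absorbs every undisproved abnormality, and the non-significant class that Sections 6.4.1 and 5.1 both rely on is empty. It is a stated rule that misclassifies if followed, not a missing detail.

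Its reach is narrow: undisproved grade 1-2 values meeting none of criteria 2 to 5. The likely harm is inconsistent low-grade laboratory counts between sites in the descriptive summary. This rests on two assumptions: that some sites apply the list literally and others do not, and that the summary is not restricted to attributable events. Nor does the text exempt all grade 1-2 values. It says only that non-significant ones generally fall there. No numerical size can be given.

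**What to change.** For AE reporting, reword Section 6.4.1 so that an abnormal value is clinically significant if it is not proved erroneous on repeat testing, where repeated, **and** meets at least one of criteria 2 to 5. Keep the grade 3 and higher rule unchanged. State the date or protocol version from which the wording applies, so that the toxicity summary can distinguish records collected under the two wordings.

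Separately, the sponsor must reconcile the Table 2 All Other Events footnote in Section 5.1 with Section 6.4.1, and say whether the footnote uses the AE-reporting definition. No hold rule is proposed here.

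The edit is one sentence and needs no new data. It does need a written amendment with CTEP and IRB approval (Section 12.2). The protocol is at Version 15.0, and Sections 2.3.8 and 2.3.9 report Stratum 1 experience already accrued, so existing AE data will remain under the current wording.
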